		5.6.1 Extent of exposure	
		5.6.2 Adverse events	
	5 7	5.6.3 Additional safety assessments	
	5.7	Subgroup analyses	
	5.8	Interim analyses	
		•	
6		porting documentation	
	6.1	Appendix 1: List of abbreviations	
	6.2	Appendix 2: Definition of exploratory efficacy/safety endpoints and assessments	19
7	Refe	rences Error! Bookmark no	t defined.

VV-TMF-5473647 | 1.0 | NN7415 - NN7415-4307

Table of tables

		Page
Table 1	Analysis sets used for analyses and/or presentations of endpoints/assessments	13

SAP NN7415-4307 week 56 3 of 29

VV-TMF-5473647 | 1.0 | NN7415 - NN7415-4307

Version history

This Statistical Analysis Plan (SAP) describes the data evaluation planned for the 56-week cut-off as mentioned in the NN7415-4307 trial protocol version 5.0 (dated 25-Mar-2021).

SAP NN7415-4307 week 56 4 of 29

04 August 2022 | Novo Nordisk Statistical Analysis Plan W56 Date: Trial ID: NN7415-4307 Version: 1.0 CONFIDENTIAL UTN: U1111-1225-9722 Status: Final EudraCT No.: 2018-004891-36 Page:

5 of 29

Introduction 1

This SAP describes descriptive analyses for the endpoints/assessments related to bleeding episodes, safety and PK/PD at the 56-week cut-off of trial NN7415-4307. The 56-week cut-off is defined as when all patients in arms 2, 3 and 4 have completed visit 13a (or permanently discontinued treatment). For a description of the analyses planned for the confirmatory analyses cut-off of the trial please refer to the SAP for the confirmatory analyses cut-off version 5.

All confirmatory conclusions for this trial are based on the analyses done at the confirmatory analyses cut-off. Therefore no further confirmatory conclusions can be made based on the descriptive analyses described in this SAP.

Additional details on the derivation and calculation based on the measurements collected in this trial will be described in the analysis data reviewer's guide (ADRG). In addition, specifications of tables, figures and listings (TFL) are described in the mock TFLs.

1.1 Objectives and endpoints

No specific objectives are defined in relation to the 56-week cut-off. For the objectives related to the confirmatory analyses cut-off, please refer to the trial protocol version 5.

All the details of the endpoints, assessments and timeframes for the 56-week cut-off are explained in appendix 2.

Statistical Analysis Plan W56
Trial ID: NN7415-4307
UTN: U1111-1225-9722

Date: 04 August 2022 | Novo Nordisk
Version: 1.0
Status: Final

Page:

7 of 29

1.2 Trial design

EudraCT No.: 2018-004891-36

The following is a brief sum up of the most important parts of the trial design. For further details refer to the trial protocol version 5.

- This is a prospective, multicentre, open label clinical trial with four arms with the aims to evaluate the effect and safety of daily concizumab prophylaxis administered s.c. in patients with HA and HB. The four arms of the trial consist of:
 - o Arms 1 and 2 consist of patients previously treated on demand who are randomised to
 - Arm 1: On-demand administration
 - Arm 2: Concizumab PPX treatment
 - o Arms 3 and 4 are allocated to receive concizumab PPX treatment and consist of
 - Arm 3: Patients that are transferred from trial NN7415-4255 (explorer 5) prior to the treatment pause
 - Arm 4:
 - Patients who have been on stable PPX at least 24 weeks in study NN7415-4322 (explorer 6)
 - Patients that were randomised to concizumab or on demand prior to the treatment pause
 - Patients that were in NN7415-4255 at the time of the treatment pause and have completed NN7415-4255 when the trial was restarted
 - Additional on demand patients included after arms 1 and 2 are closed
- In the second quarter of 2020, the protocol was amended (protocol version 4.0) to incorporate measures to mitigate the risk of thromboembolic events. These measures include the handling of factor treatment for breakthrough bleeds and changes to the dosing regimen. As a result of these changes and the pause in the treatment while the protocol was to be amended, all statistical analyses were reconsidered and adjusted accordingly.
- The confirmatory analyses are made when all patients in arm 1 have completed visit 9/9a (or withdrawn) and all patients in arm 2 and 4 have completed visit 10a (or withdrawn).
- After the main part of the trial, all patients have been offered to continue in the extension part of the trial and receive treatment with concizumab for up to an additional 128 weeks (arms 2–4) or 136 weeks (arm 1)
- After 56 weeks of treatment in arms 2, 3 and 4, an additional evaluation will be made assessing bleeding episode related endpoints and safety for concizumab. This SAP describes in more detail the descriptive analyses that are relevant for this cut-off.

2 Statistical hypotheses

For the analyses related to the 56-week cut-off no statistical hypotheses are tested.

SAP NN7415-4307 week 56 8 of 29

3 Sample size determination

The sample size considerations are described in detail in section 10.1 of the protocol version 5.

SAP NN7415-4307 week 56 9 of 29

Statistical Analysis Plan W56 Trial ID: NN7415-4307 UTN: U1111-1225-9722 EudraCT No.: 2018-004891-36

CONFIDENTIAL

Date: Version: Status: Page:

04 August 2022 | Novo Nordisk Final 10 of 29

Analysis sets 4

For the purposes of analysis, the following analysis sets are defined for the 56-week cut-off.

Subject Analysis Set	Description
Full Analysis Set (FAS)	All patients randomised to the new concizumab PPX dosing regimen or on-demand treatment after the treatment pause or allocated to arm 3 or 4 with the new concizumab PPX dosing regimen. Patients from arms 1 and 2 will contribute to the evaluation 'as randomised'.
Safety Analysis Set (SAS)	All patients exposed to concizumab PPX or randomised to on-demand treatment. All patients will contribute to the evaluation 'as treated'.

Defined Analysis Data Sets	Description
On-treatment	The time period where patients are considered to be affected by on- demand treatment or concizumab treatment.
	For safety endpoints/assessments relating to events (number of thromboembolic events, number of hypersensitivity type reactions, number of injection site reactions, number of patients with antibodies to concizumab, number of adverse events) the 'on-treatment' analysis data set is defined as follows.
	For patients in arm 1 (before or after restart) during on-demand treatment, the period begins on the date of randomisation (as registered in IWRS) and ends at the first occurrence of:
	 Time of permanently ending on-demand administration and the day before initiation of any PPX regimen The last direct patient-site contact, at or prior to the 56 weeks cut-
	 off Withdrawal date for patients who withdraw informed consent The last patient-investigator/site contact as defined by investigator for patients who are completely lost to follow up Date of death for patients
	For patients in arm 1 during concizumab PPX treatment , the period begins at the time of initiation of concizumab PPX treatment and ends at the first occurrence of:
	 6. Date of last dose of concizumab + 7 weeks 7. Items 2., 3., 4. or 5. Above

Statistical Analysis Plan W56 Trial ID: NN7415-4307 UTN: U1111-1225-9722 EudraCT No.: 2018-004891-36

CONFIDENTIAL

Date: Version: Status: Page:

04 August 2022 | Novo Nordisk 11 of 29

Final

For all patients randomised/allocated to arm 2-4 either before or after the treatment pause:

- For patients only exposed to the initial concizumab PPX dosing regimen the period begins at the start of the initial concizumab PPX regimen and ends at the first occurrence of items 2-6 above
- For patients only exposed to the new concizumab PPX dosing regimen the period begins at the time of start of the new concizumab PPX dosing regimen and ends at the first occurrence of items 2-6 above
- For patients exposed to both the initial and the new concizumab PPX dosing regimen the period consists of two parts with a pause in between. The first period begins at the time of start of the initial concizumab PPX dosing regimen and ends 7 weeks after concizumab treatment was paused while the second period begins at the time of start of the new concizumab PPX dosing regimen and ends at the first occurrence of items 2-6 above

Note that patients randomised to arm 1 or 2 before the treatment pause will be allocated to arm 4 after the restart and will fall in either of the three groups above when treated with concizumab.

For all other endpoints/assessments the 'on-treatment' analysis data set is defined similarly as above with the exceptions that:

The addition of 7 weeks to the date of last dose of concizumab is instead set to 1 day

On-treatment without data before restart

The time period after the restart where patients are considered to be affected by on-demand treatment or treatment with the new concizumab dosing regimen.

The analysis data set is defined similarly as the 'on-treatment' analysis data set with the exception:

Observation time before restart is excluded

On-treatment without ancillary therapy^a excl. data before restart

The time period after the restart where patients are treated by concizumab treatment or are treated by on-demand treatment and additionally have not used factor-containing products not related to treatment of a bleeding episode.

The analysis data set is defined similarly as the 'on-treatment' analysis data set with the exception:

- Observation time before restart is excluded
- Periods where factor containing products not related to a bleeding episode have been used are excluded

SAP NN7415-4307 week 56 12 of 29

^a Ancillary therapy is defined as use of factor-containing products not related to treatment of a bleeding episode except when used in relation to diagnostic procedures, intramuscular injections and minor surgery.

Statistical Analysis Plan W56 Trial ID: NN7415-4307 UTN: U1111-1225-9722

EudraCT No.: 2018-004891-36

CONFIDENTIAL

Date: Version: Status: Page:

04 August 2022 | Novo Nordisk Final 13 of 29

Statistical analyses 5

General considerations 5.1

This SAP will address the details of the descriptive statistics implemented on all arms (1, 2, 3 and 4) at the 56-week cut-off of trial NN7415-4307. The 56-week cut-off is defined as when all patients in arms 2, 3 and 4 have completed visit 13a (or permanently discontinued treatment).

In general, all TFLs will differentiate between HA and HB patients. For some endpoints/assessments HA and HB may be pooled.

Unless specified otherwise, the endpoints/assessments will be presented using the analysis sets as displayed in Table 1.

Table 1 Analysis sets used for analyses and/or presentations of endpoints/assessments

Endpoint/assessment categories ^a	Subject Analysis Set	Analysis Data Sets
Bleeding episodes	FAS	On-treatment without ancillary therapy excl. data before restart
PK, PD and safety not relating to events	SAS	On-treatment without data before restart
Safety relating to events ^b	SAS	On-treatment and On-treatment without data before restart

^aWhich endpoints/assessments that belong under each category can be found in section 9 of the protocol version 5. ^bThis specifically refers to: number of thromboembolic events, number of hypersensitivity type reactions, number of injection site reactions, number of patients with antibodies to concizumab, and number of adverse events.

Continuous endpoints/assessments will be presented using descriptive statistics which will include min, max, mean, SD, median, and quartiles. For PK endpoints/assessments, the descriptive statistics will also include geometric mean and CV. Event data (including AEs) will be summarised including number of patients with an event/episode, percentage of patients with an event/episode, number of events/episodes and rate of events/episodes. Categorical assessments will be summarised by number and percent of patients in each category.

Presentations of results will be by arm and visit (when applicable) and when relevant arm 1 will be split into two parts with on-demand treatment and concizumab treatment.

Event data relating to safety where the 'on-treatment' analysis data set is used will include both data on the initial and the new concizumab dosing regimen.

Baseline after the pause is defined as the latest measurement recorded before the start of the new concizumab dosing regimen (arms 2-4 and arm 1 concizumab part) or recorded before randomisation to the on-demand administration (arm 1) after the pause. If this measurement is missing, then the latest measurement recorded before the start of the initial concizumab dosing regimen (arms 2-4) or recorded before the on-demand randomisation before the pause (previous arm 1 (now arm 4) on-demand part) will be used (if available).

Baseline for the period before the treatment pause is defined as the latest measurement recorded before the start of the initial concizumab dosing regimen (arms 2-4) or recorded before the ondemand randomisation (arm 1 on-demand).

The target joints at baseline will be used for the definition of target joint bleeds.

In terms of bleeding episode related endpoints, the bleed rate is defined as the number of bleeding episodes over the respective observation periods. Multiple bleeding locations at the same time point will be counted as one bleeding episode. As a general rule, a treated bleeding episode is defined as any bleeding episode where the use of a factor-containing product is reported between the start and stop time of a bleed. Further, the endpoints will not include re-bleeds. A re-bleed is defined as a bleed (worsening of bleeding site conditions e.g. swelling, pain) starting within 72 hours after stopping treatment of a previous treated bleed (or re-bleed) at the same anatomical location. Note that there can be more than one re-bleed related to the same bleed. If a bleed occurs in the same location more than 72 hours after stopping treatment of a previous bleed (or re-bleed) in the same location, the bleed is defined as a new bleeding episode.

Pharmacokinetic concentration values below lower limit of quantification (LLOQ) is handled as described below:

Timing of values below LLOQ	Imputation	Use of imputed
		values
Values below LLOQ obtained before time of the first administration with concizumab and the predose measurement collected at restart for those patients who restarts	Set to 0 (zero)	Plots
All other values below LLOQ	Set to LLOQ/2	Plots

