The concizumab clinical development programme in patients ≥12 years of age comprises four phase 1 trials, two phase 2 trials, two phase 3 trials and a non-interventional study. Details on the individual trials are provided in the IB. Phase 3 clinical trials were initiated in October 2019; trial NN7415-4307 (explorer 8) in patients with HA and HB and trial NN7415-4311 (explorer 7) in patients with HAwI and HBwI. In February and March 2020, 5 serious thromboembolic events were reported in 3 patients included in the phase 3 trials (2 patients in trial 4307 and 1 patient in trial 4311). As a result of the occurrence of these events, clinical development was paused and investigations to understand what may have contributed to the non-fatal thromboembolic events were conducted. The findings from the investigations have led Novo Nordisk to implement a number of changes to the trial protocols (as reflected by this protocol amendment (protocol version 4.0)) to reduce the risk that additional patients treated with concizumab will experience thromboembolic events. The changes have been accepted by the external independent Data Monitoring Committee.

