No significant thromboembolic events or signs of DIC were reported in the phase 1 or phase 2 concizumab clinical trials with an exposure time of up to 102 weeks for the individual patient in the phase 2 trials. After initiation of the phase 3 clinical trials, 5 serious thromboembolic events (all non-fatal) were reported in 3 patients; the events were of different pathological aetiology, i.e. arterial and venous. All events occurred within 3 months of concizumab treatment initiation. All 3 patients experiencing thromboembolic events had different types of thromboembolic risk factors and all 3 patients had used breakthrough bleed treatment just before the onset of symptoms for the thromboembolic event. In 2 of the cases, either a relatively high dose or prolonged treatment with factor product was reported. The concizumab exposure levels for these 2 patients were also among the highest levels observed across the phase 2 trials (4310 and 4255) and the phase 3 trials (4307 and 4311), and it was also noted that overall, the concizumab exposure levels in phase 3 at the 0.25 mg/kg dose-level were higher than expected. For the remaining patient, a possible/potential renal infarct prior to trial entry is being assessed (not confirmed). The findings from the investigations of the cases have led Novo Nordisk to make several changes to the trial protocols to reduce the risk that additional patients treated with concizumab will experience thromboembolic events.

These changes include:

- A new guidance for treatment of mild and moderate breakthrough bleeds, with specific guidance for use of the lowest dose of factor product or bypassing agent while on concizumab PPX (see Section 5.2.3).
- That patients **must** contact the site when they have a suspected bleed (see Section 5.2.3).
- Continuation of previous PPX for up to two weeks after initiation of concizumab dosing is no longer allowed (see Section 5.2.1)

• A new concizumab dosing regimen including an initial daily dose of 0.20 mg/kg concizumab (instead of 0.25 mg/kg). Criteria for an increase or decrease in the daily maintenance dose to 0.25 mg/kg or 0.15 mg/kg, respectively (based on concizumab exposure levels at the week 4 visit) are provided. The loading dose remains 1.0 mg/kg (see Section 5.2.1).

- Elective major surgery is no longer allowed (see Section 9.9).
- Trial stopping rule requiring urgent evaluation by the Novo Nordisk Safety Committee and

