5.6.2 Adverse events

All exploratory safety endpoints are defined in section 6.2.

All adverse events will be coded using the current version of MedDRA. Hypersensitivity reactions, medication errors and injection site reactions are categorised in the CRF as AEs requiring additional data collection. Additional information on these events will be collected using separate forms. Further, a MedDRA search will also be used to define these events. Thromboembolic events are defined and categorised as AESIs.

Adverse events will be evaluated using descriptive statistics based on the analysis data sets as described in section 5.1. The outputs will differentiate between haemophilia type.

Furthermore, for the on-treatment analysis data set the outputs on adverse events will also include information on

- System organ class
- Severity (mild/moderate/severe), seriousness (serious/non-serious) and relation to treatment (possibly/probably/unlikely)
- Adverse events leading to drug discontinuation
- Most frequent adverse events (occurring in more or equal to 5% of patients)
- Deaths
- Medication errors

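### Thromboembolic events are summarised with no breakdown by time since starting concizumab, although all events known at restart came within 3 months of initiation

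*SAP*

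**What the plan says.** SAP section 5.1 summarises event data by the number and percentage of patients with an event, together with "number of events/episodes and rate of events/episodes", presented by arm and generally by haemophilia type. SAP section 5.6.2 adds: "Adverse events will be evaluated using descriptive statistics based on the analysis data sets as described in section" 5.1, with further breakdowns by organ class, severity, seriousness, relatedness, discontinuation and death. SAP Appendix 2 lists the number of thromboembolic events as a count.

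Table 1 of the SAP gives two data sets for safety events. One covers both regimens together and the other leaves out data before restart. For patients exposed to both regimens, SAP section 4 says the first period "ends 7 weeks after concizumab treatment was paused"; the second runs to the 56-week cut-off unless it ends earlier. SAP section 5.6.1 reports the lengths of the periods. No section splits events or exposure by time since first dose, plans a cumulative incidence, or shows the initial regimen alone.

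Protocol section 3.2 reports that "5 serious thromboembolic events were reported in 3 patients included in the phase 3 trials" (two patients in this trial, one in the sister trial) and that "Phase 3 clinical trials were initiated in October 2019". Protocol section 3.3 says: "All events occurred within 3 months of concizumab treatment initiation". It adds that "all 3 patients had used breakthrough bleed treatment just before the onset of symptoms".

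**The concern.** An overall rate describes risk well when the hazard is roughly constant. The protocol's own account of the events gives reason to doubt that here. If most of the risk lies in the first months, each further month of event-free follow-up lowers the rate without saying anything about risk at initiation.

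Follow-up differs sharply between regimens. Phase 3 began in October 2019 and the pause started in March 2020, so patients who started concizumab in phase 3 had at most about 5 to 6 months on the initial regimen. Completers in arms 2-4 have at least 56 weeks on the new one. A pooled rate and a new-regimen-only rate will sit in the same report, and readers will compare them when judging whether the restart measures worked. The planned outputs do not let them separate a change in early risk from a change in length of follow-up.

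**Working it through.** The documents give no thromboembolic rate or person-time, so there is no planned figure to reproduce. The check is how an overall rate behaves under stated assumptions.

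**Inputs.** Early window: 3 months (protocol 3.3), taken as 13 weeks. New-regimen follow-up T: 56 weeks (SAP 5.1), with 104 weeks assumed as an upper case for early enrolees. Initial-regimen dosing e: 8, 13 or 22 weeks assumed, plus the 7-week tail (SAP 4). Later hazard as a fraction f of the early hazard: 0, 0.1 or 0.25, assumed. The rate denominator is assumed to be total period length, since the SAP defines a rate only for bleeds.

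**Step 1, dilution of one rate.** Overall rate ÷ early rate = (13 + f(T − 13))/T.
- T = 56: 13/56 = 0.23 (f = 0); (13 + 4.3)/56 = 0.31 (f = 0.1); (13 + 10.75)/56 = 0.42 (f = 0.25).
- T = 104: 0.13, 0.21 and 0.34.
- f = 1 (constant hazard): 1 at any T, so no fall.

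**Step 2, two regimens with the same early hazard.** This is an illustration, because the plan shows no initial-regimen-only rate. Taking no hazard in the tail, the initial-regimen factor is (min(e,13) + f·max(e − 13, 0))/(e + 7).
- f = 0: initial factors are 8/15 = 0.53, 13/20 = 0.65 and 13/29 = 0.45. New/initial ratios run from 0.125/0.65 = 0.19 (T = 104) to 0.232/0.448 = 0.52 (T = 56), where equal risk should give 1.
- f = 0.25: initial factors are 0.53, 0.65 and 15.25/29 = 0.53. Ratios run from 0.344/0.65 = 0.53 to 0.424/0.526 = 0.81.

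The pooled set contains the new-regimen data, so the gap between the two planned rates would be smaller than these ratios.

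**Step 3, could the early clustering come from the pause?** Assume uniform entry over 17 to 26 weeks before the pause. The share of initial-regimen dosing time in the first 13 weeks is then 0.945 (17 weeks) to 0.75 (26 weeks). Under a constant hazard, all 3 patients would have early events with probability 0.945³ = 0.84 to 0.75³ = 0.42. The observed pattern fits either explanation.

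**The case against.** A reader might infer that thromboembolic events will be shown only as one average rate, and that the new regimen's rate must fall several-fold through longer follow-up alone. The documents support neither inference. The SAP also plans the percentage of patients, which extra event-free follow-up does not dilute, and it reports period lengths. The fall depends on an early-weighted hazard, and step 3 shows that the clustering may reflect truncation. No comparison of regimens is planned, no hypothesis is tested at this cut-off, and no further confirmatory conclusion is allowed. Nor is all pre-pause exposure early: arm 3 patients came from phase 2 already on concizumab. Safety decisions do not wait for this table either, because single significant events trigger urgent review (protocol 9.3.9) and a monitoring committee sees accumulating data. With two affected patients in this trial, an exact Poisson 95% interval spans 0.24 to 7.2 events, about 30-fold. Mock tables and the SAP for the confirmatory cut-off are not available here and might hold more.

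Most of this stands, and it limits the claim. It does not remove the gap. Percentages in arm 2, and in arm 1 on concizumab, come from new, previously on-demand patients and are useful, but they have no separate initial-regimen counterpart and do not divide early from late events. Elsewhere percentages are harder to read. Some initial-regimen patients were stopped before 13 weeks. Arms 3 and 4 include patients with earlier concizumab exposure, and because a significant event requires stopping treatment (protocol 8.1), restarters had largely come through that exposure without one. SAP 5.6 also presents pre-pause arm 2 data as arm 4 for those who restarted. The possible truncation artefact is itself a reason to split exposure by time. Up to 102 weeks in phase 2 without significant thromboembolic events lends some support to early clustering, though dosing and bleed guidance differed.

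**Conclusion.** The point holds as a gap in the planned safety summaries. The protocol ties the known events to the first 3 months, and nothing in the SAP text shows events or exposure by time since start. The size is conditional: at 56 weeks the overall rate is 0.23 to 0.42 of the early rate if the later hazard is 0 to 25% of the early one, and it is undiluted if the hazard is constant. To the extent that risk is early, the pooled and new-regimen-only rates are not comparable.

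This rests on 13 weeks for 3 months, total period length as the rate denominator, and assumed values for f and for follow-up beyond 56 weeks. It does not show that the new regimen's rate will be biased by any given factor, or that the sponsor intends to claim lower risk from this rate. It is an inexpensive improvement to a descriptive analysis.

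**What to change.** In SAP section 5.6.2, keep the planned summaries and add:
- A table of patients with thromboembolic events, number of events and exposure time by window since start of concizumab (weeks 0-13, after week 13), with a cumulative-incidence curve.
- Both shown separately for the initial and the new regimen and, within the new regimen, separately for concizumab-naive patients and those with earlier exposure (arm 3, restarters already dosed before the pause, former explorer 5 patients). Without this last split, time since first dose of the new regimen would label previously exposed patients as newly exposed.
- A listing giving, for each event, the time since first-ever concizumab dose, since first dose of the current regimen, and since the last factor dose.

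The cost is one table, one figure and one listing. Treatment dates, adverse-event records and factor-dose times are already collected, and earlier explorer 5 dosing dates would come from that trial. Nothing here is confirmatory, so there is no alpha cost. The downside is few events per cell and wide intervals, which the outputs should show.
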